As rapid, molecular diagnostic tests for gonorrhea and chlamydia are becoming available, providing a test result within the time frame of a clinical encounter will become increasingly feasible in the near future. Decreasing the time from specimen collection to STI test result with point-of-care tests has the potential to avoid inappropriate antibiotic treatment, decrease forward STI transmission, and reduce costs.^{7,10,11} Thus, it is critical to understand the potential impact of rapid molecular tests on STI management in

specialized STI clinics, which in turn can inform the implementation of point-of-care molecular STI testing in other clinical settings.

The binx *io* is an FDA-approved desktop polymerase chain reaction (PCR) platform for the detection of the etiologic agents of gonorrhea and chlamydia using self-contained cartridges. The platform is CLIA certified and can be set up at the point of care (e.g., within a clinic) and operated by staff without formal laboratory training. The hands-on time of specimen processing is approximately one minute, and qualitative (positive/negative/invalid) results for gonorrhea and chlamydia infection are available in 30 minutes. The platform has demonstrated good sensitivity and specificity for the detection of gonorrhea and chlamydia from male urine or female vaginal swab specimens.¹²

The binx *io* platform has the potential to inform the clinical management of urethritis and cervicitis beyond that of the point-of-care gram stain. The sensitivity and specificity of the binx *io* should allow for a similar detection rate of gonococcal urethritis or cervicitis as with the point-of-care gram stain. In addition, the binx *io* can detect the presence of chlamydia, which can have a direct impact on the antibiotics administered for immediate management of symptomatic urethritis or cervicitis during the clinical encounter. Specifically, with a negative chlamydia result on the binx *io*, patients may be spared from the empiric use of antibiotics for chlamydia. Additionally, an in-clinic diagnosis of chlamydia would allow patients with an indication for expedited partner therapy (EPT) to receive a prescription for partner therapy earlier, decreasing treatment delay among their partners. However, the impact of the binx *io* on management of urethritis and cervicitis has not yet been studied in a specialized STI clinic setting.

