This study is a pilot randomized controlled trial evaluating the use of either a) the binx *io* or b) point-of-care gram stain (current standard of care) to guide clinical management of patients with symptomatic urethritis or cervicitis evaluated in the MGH Sexual Health Clinic. Patients presenting with symptoms of urethritis or cervicitis and meeting inclusion criteria will be randomized to have diagnostic specimens tested during the clinical encounter using either the binx *io* platform or point-of-care gram stain. Patients randomized to the intervention arm of the study will also have a gram stain slide created, which will be held for later interpretation following the clinical encounter. Participants will not be followed longitudinally. Towards the end of the study, we will conduct a focus group discussion with Sexual Health Clinic staff to explore their impressions of use of a rapid STI test in the clinic and other potential uses of rapid STI testing in STI clinical management.

A detailed study schema is attached.

4. Subject Selection

The study will take place in the Massachusetts General Hospital Sexual Health Clinic (SHC), a specialized sexually transmitted infection (STI) clinic operated in partnership with the Massachusetts Department of Public Health. The clinic is staffed by nurse practitioners and physicians, who see patients for scheduled and urgent care visits.

Potential participants will be identified for recruitment by the Sexual Health Clinic staff upon review of the reasons given for scheduled or urgent care appointments for the day. Additionally, any patient who reports symptoms of urethritis or cervicitis during the clinic encounter, regardless of the reported chief complaint for the visit, will be assessed for eligibility by the clinician. Participants will be approached by a research assistant to introduce the study and obtain informed consent. Consenting participants will be

randomized to either the intervention or control group using a randomization function in RedCap.

Patients presenting to the Sexual Health Clinic will be eligible to participate in the study based on the following criteria:

Inclusion criteria

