6. STUDY PROCEDURES

All study procedures will take place during the patient's index clinic visit. All participants will undergo routine evaluation and specimen collection per current clinic protocols. This includes a pelvic exam and self-collected or clinician-collected endocervical swabs for female participants; or a genital exam and clinician-collected urethral discharge specimen for male participants per standard clinic collection protocols. For participants randomized to the intervention arm, either one vaginal swab (female participants) or urine sample (male participants) will be collected for testing by the binx platform.

The endocervical and urethral specimens collected for use in this study will be processed immediately for point-of-care gram stain and additional specimen plated for gonorrhea culture as per current clinic protocols; to be sent to the Massachusetts Department of Public Health (DPH). Additional specimens will be sent to the DPH for nucleic acid amplification testing (NAAT) for gonorrhea and chlamydia, as per current clinic protocols. Participants in both the control and intervention arm of the study will have a point-of-care gram stain created, from either vaginal or endocervical swab (for female participants) or urethral swab (for male participants). All point-of-care gram stains will be performed by staff up to date with proficiency testing as per the MGH point of care testing committee. The point-of-care gram stain requires approximately 5-10 minutes for specimen processing/creation of the gram stained slide and reading of the slide. The point-of-care gram stain will be processed and read in the Sexual Health Clinic laboratory space on Cox 5 (room #572). Participants in the control arm will be administered antibiotic therapy in the clinic based on the results of the point-of-care gram stain. Point-of-care gram stain slides for intervention arm participants will be held for later interpretation following the clinical encounter. The gram stain slides from intervention arm participants each week will be labelled with the participant's study number and read at the end of the week. Results will be recorded in the study record.

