For participants randomized to the intervention arm, the aliquot of urine (male participants) or the vaginal swab (female participants) will be processed immediately for testing on the binx *io* platform. All point-of-care testing will be conducted in the Sexual Health Clinic laboratory space on Cox 5 (room #572). The MGH Point of Care testing committee will guide the process of quality control for the binx *io* platform.

Participants will be administered antibiotic therapy in the clinic based on results of the point-of-care gram stain in the control arm and according to the binx io results in the intervention arm. A positive gram stain for gonorrhea will be defined using standardized clinical criteria, consisting of >4 polymorphonuclear leukocytes (PMNs) per high power field for male specimens and >10 PMNs per high power field for female specimens, along with the presence of intracellular gram-negative diplococci. Treatment for chlamydia, which cannot be detected specifically by the point-of-care gram stain, will be administered per routine clinical practice (either treated empirically or deferred pending confirmatory testing at the Massachusetts DPH) per the discretion of the clinical provider per routine clinical procedures. Results on the binx io are qualitative, indicating either the presence or absence (positive or negative result) separately for gonorrhea and chlamydia. For participants with positive test results for chlamydia on the binx io platform, the participant will be counseled on the availability of Expedited Partner Therapy (EPT) as per standard clinical guidelines. The results of binx io testing and treatment administered will be recorded in the medical record. For participants who are unwilling or unable to wait for the results of the binx io, clinical management will be at the discretion of the treating clinician and can involve the interpretation of the prepared and stored gram stain if elected by the treating clinician.

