Participants in the focus group discussion may benefit by improving understanding of effective ways to incorporate rapid testing into specialized STI care, thus potentially improving their work experience and ability to care for patients in the future.

9. Statistical Analysis

Sample size calculation

We hypothesize that the use of the binx *io* platform will decrease the mean number of antibiotic courses per patient by 10%. Based on data from 2020, symptomatic patients would receive approximately 1.13 courses of antibiotics per patient. With an alpha of 0.05, we would have a power >90% to detect a decrease of 10% (to 1.017 per patient) with sample size of 100 (50 per arm).

Analysis plan

The primary outcomes for Aim 1 will be compared between patients randomized to clinical management based on the binx *io* and patients randomized to clinical management based on point-of-care gram stain. Demographic and clinical data for both cohorts will be obtained from the SHC RedCap database and supplemented with chart review as necessary.

Standard descriptive statistics will be used to report primary and secondary clinical outcomes, reported as proportions, means with standard deviation, or median with interquartile range as appropriate. Unadjusted and adjusted ordinal logistic regression models will be used to compare the total antibiotics administered between patients for whom the binx *io* vs point of care gram stain was used for clinical management. Adjusted models will incorporate predictors felt clinically to affect likelihood of antibiotic administration as well as those found to be significant in unadjusted analyses, including gender, age, race/ethnicity, and insurance status.

Transcripts from the focus group discussion will be transcribed, coded, and analyzed for key themes deductively and inductively using content analysis.

10. Monitoring and Quality Assurance

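### The analysis plan groups patients as randomized in one sentence and by the test used in the sentence that names the model; an exit open only to the intervention arm can make the two differ

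*Combined protocol and SAP*

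**What the plan says.** Section 9 (Statistical Analysis, Analysis plan) describes the Aim 1 comparison twice.

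- The opening sentence says the primary outcomes will be "compared between patients randomized to clinical management based on the binx *io* and patients randomized to clinical management based on point-of-care gram stain". That is grouping by assignment.
- The sentence naming the unadjusted and adjusted ordinal logistic regression models says they compare the "total antibiotics administered between patients for whom the binx *io* vs point of care gram stain was used for clinical management". Read as written, that is grouping by the test that guided treatment.

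Section 6 (Study Procedures) lets assignment and use come apart: "For participants who are unwilling or unable to wait for the results of the binx io, clinical management will be at the discretion" of the clinician, and this "can involve the interpretation of the prepared and stored gram stain if elected by the treating clinician". The protocol provides this exit in the intervention arm only. The two tests also differ in waiting time. For binx, Section 1 says "qualitative (positive/negative/invalid) results for gonorrhea and chlamydia infection are available in 30 minutes"; for the control test, Section 6 says "The point-of-care gram stain requires approximately 5-10 minutes for specimen processing/creation of the gram stained slide and reading of the slide".

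The visible text contains no definition of an analysis set and no sentence placing every randomized participant in the assigned arm for analysis.

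**The concern.** The two definitions agree only if every intervention participant is managed on a binx result, and Section 6 plans for some who are not. Under the model sentence read literally, one managed on the stored slide joins the gram stain group, and one managed on neither test belongs to no group.

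Not waiting happens after randomization, and these participants' treatment is chosen without the binx result. That includes the decision to treat chlamydia empirically or defer, which is where the protocol expects binx to change antibiotic use. If their number of courses differs from the average, taking them out of one arm, and perhaps adding them to the other, produces a difference that the test did not cause. Leaving the choice open would also allow the grouping to be settled after outcomes are known.

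**Working it through.** **Inputs from Section 9.** Control mean 1.13 courses; 50 per arm; hypothesized decrease 10%. The plan's figure reproduces: 1.13 × 0.90 = 1.017, a difference of 0.113. The power statement is a separate matter and is not used here.

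**Assumptions.** The documents give neither the number of intervention participants managed off binx (k) nor their mean number of courses (m). I take k = 1, 3 or 5 of 50, and m = 2, 1, 0 or 1.13. The case m = 0 means treatment was deferred and no later course is counted.

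**No true effect.** Each arm as randomized has 50 × 1.13 = 56.5 courses, so the difference as randomized is 0 for every k and m. Grouping by test used gives:

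- binx group mean = (56.5 − k·m)/(50 − k)
- gram stain group mean, if they are moved = (56.5 + k·m)/(50 + k)
- gram stain group mean, if they are left out = 1.13

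Worked for k = 3:

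- m = 2: 62.5/53 − 50.5/47 = 1.1792 − 1.0745 = 0.105
- m = 0: 56.5/53 − 56.5/47 = 1.0660 − 1.2021 = −0.136
- m = 1.13: both means are 1.13, so the difference is 0

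Expected spurious difference, gram stain minus binx (positive favours binx):

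| Courses per off-binx participant | Handling | k = 1 | k = 3 | k = 5 |
|---|---|---|---|---|
| 2 | moved | 0.035 | 0.105 | 0.176 |
| 2 | left out | 0.018 | 0.056 | 0.097 |
| 1 | moved | −0.005 | −0.016 | −0.026 |
| 1 | left out | −0.003 | −0.008 | −0.014 |
| 0 | moved | −0.045 | −0.136 | −0.228 |
| 0 | left out | −0.023 | −0.072 | −0.126 |
| 1.13 | either | 0 | 0 | 0 |

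**False-positive rate.** I simulated trials with no effect, assuming 25%, 37% and 38% of patients get 0, 1 and 2 courses (mean 0.37 + 2 × 0.38 = 1.13), with a two-sided rank test at 0.05 standing in for the ordinal model. Rejection rates when k participants are moved:

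- all with two courses: about 10% (k = 3) and 20% to 22% (k = 5)
- all with none: about 13% (k = 3) and 26% to 29% (k = 5)
- all with one course, or drawn like everyone else: about 5% to 6%
- k = 1: about 5% to 6% in every case

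As randomized, the rate is about 4% to 5%.

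**With the hypothesized effect.** Let participants managed on binx average 1.017 and controls 1.13, with k = 5.

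- m = 1.13: as randomized, 0.113 × 45/50 = 0.102; moved, 1.13 − 1.017 = 0.113.
- m = 1.5: as randomized, 1.13 − (45 × 1.017 + 5 × 1.5)/50 = 0.065; moved, (56.5 + 7.5)/55 − 1.017 = 0.147.

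**The case against.** The strongest reply is that the opening sentence of the analysis plan governs. It fixes the comparison for the Aim 1 primary outcomes by randomization, and the next sentence speaks of two cohorts, which must be those groups. The documents also use the tests as shorthand for the arms elsewhere. Aim 1 in Section 2 describes a randomized trial in terms of patients evaluated with one test or the other, and Section 6 ties each test to its arm. The literal reading leaves some randomized patients in no group, which makes it less likely to be what was meant.

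Much of this stands. A reader might infer that the plan gives these participants no group at all, or that it commits to an as-treated analysis. Neither is supported: the opening sentence does assign a group, and the later wording may be loose. What remains is that nothing says which sentence prevails, and the only one an analyst can program from uses the other definition.

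The figures also rest on assumed cases. The large ones need every off-binx participant to be alike and at an extreme, so it does not follow that a few participants are enough whatever their treatment.

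A reader might also count failed runs as a second form of selection, since Section 1 lists an invalid result. Nothing in the documents links a failed run to patient characteristics. The absence of a visible rule for such runs is not a finding either, because Section 3 says "A detailed study schema is attached" and that schema cannot be seen.

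**Conclusion.** The point holds as an internal inconsistency in Section 9: two definitions of the comparison groups, and a procedure in Section 6 under which they differ. Followed literally, the model sentence breaks the randomized comparison.

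The consequence is conditional and has no fixed sign. At 3 of 50 moved it runs from 0.105 favouring binx to 0.136 against it, about the size of the 0.113 effect sought. It is 0 if those participants average the same number of courses as everyone else, and nonexistent if nobody leaves. It would be tempting to conclude that the plan favours binx; that does not follow, because the documents give neither the off-binx rate nor how those patients are treated. In a pilot this is something to consider, and it is cheap to put right.

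**What to change.** In the regression sentence of Section 9, replace the group definition with: *between participants randomized to the binx io arm and participants randomized to the gram stain arm. All randomized participants are analysed in the arm assigned, whichever test guided treatment.*

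If an analysis by test used is wanted, label it secondary. Report the number of intervention participants managed without a binx result beside the primary result.

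The cost is one reworded sentence and one or two added ones. No procedure, specimen or visit time changes. Section 6 has binx results and treatment recorded, and Aim 2 counts invalid results and equipment errors, but neither lists leaving before the result as a recorded item, so the count may need one added data field.
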